to the developmental process of aging and cognition, fueled in part by the partial overlap of pathological markers and decline in mnemonic function observed in a substantial proportion of 'normal' aged individuals (Mohs et al., 1998; Whalley, 2002). As shown in Figure 1, a total of 296 participants were recruited for Wave 1 from 2008 to 2014 to the DLBS and they received cognitive testing, structural and functional MRI, as well as a scan for beta amyloid using the radioligand AV-45 (florbetapir F 18, also known as "[¹⁸F]AV-45"). A total of 183 returning participants were tested four years later in Wave 2, and they received the same battery (shown in Figure 2) as in Wave 1. In addition, 60 of these were also scanned with Flortaucipir F 18 (also known as "[¹⁸F]AV-1451"). [¹⁸F]AV-1451 is a newly-developed Phase II ligand that measures tau deposit in the human brain and this drug was provided to the DLBS by Avid Radiopharmaceuticals.

The objective of the current project is to manufacture [¹⁸F]AV-1451 (Flortaucipir F 18) at the University of Texas Southwestern Medical Center (UTSW) for use in Wave 3 of the DLBS. We will offer an AV-1451 PET scan to past Wave 1 and 2 participants. We will first contact those who completed Waves 1 and 2, followed by those who completed only Wave 1 until we have used the 125 doses we were allocated. Figure 3 shows the specific procedures associated with this protocol for the up to 125 participants who will receive tau imaging in Wave 3. The inclusion of tau imaging in Wave 3 will allow us to relate tau deposition in the brain to the 10-year history of amyloid deposition and cognitive decline in the DLBS participants and understand the independent and joint contributions of tau to cognitive decline and early AD at different ages.

Figure 1. Dallas Lifespan Brain Study Overview and Timeline

[figure not shown]
The DLBS is an ongoing, comprehensive study of the relationship between brain structure and function to decline in cognition across the lifespan. The focus of this protocol is noted in, "DLBS Wave 3."

DLBS Wave 1					
Study Information Measures Collecte					
•	464 Typically-healthy adults were recruited to participate Enrollment and testing occurred from 2008-2014 Ages: 30-89	-Detailed Cognitive Battery -Structural MRI -Functional MRI -Florbetapir (F18) PET Imaging -0 participants with AV-1451 PET imaging			
	DLBS \	Nave 2			
	Study Information	Measures Collected			

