6.4.4. Rationale

Tau pathology is a primary feature of Alzheimer's disease, and can now be measured in vivo using the recently developed PET radiotracer [¹⁸F]AV-1451. Autopsy studies have long established that many older adults who exhibited no signs of cognitive impairment in life are found at autopsy to possess the neuropathological hallmarks of Alzheimer's disease: amyloid plaques and neurofibrillary tau tangles. In the previous decade, PET imaging tracers made it possible to image amyloid plaques but not tau tangles in the living brain, providing substantial insight into the cascade of events leading from a healthy to a diseased brain. However, these studies have also indicated that amyloid has a limited direct effect on the neurodegeneration and cognitive decline indicative of incipient dementia. One prevailing theory, supported by in vivo measures of amyloid and tau, is that amyloid induces tau tangle pathology, and it is tau that directly connects to neurodegeneration and cognitive decline. The recent development of tau imaging ligands, including [¹⁸F]AV-1451, provides an opportunity to better understand the joint influence of tau and amyloid on neurodegeneration and cognition, as well as insight into the neurological cascade from health to dementia of the Alzheimer's type. An understanding of this cascade is critical for therapeutic and intervention trials.

The main objective of the present project is to assess evidence for neurofibrillary tau pathology in the brains of adults who are participants in Wave 3 in a larger project — the DLBS. This is a longitudinal observational study and tau imaging will be open-label. The DLBS protocol includes structural MRI, diffusion tensor, functional MRI, and a comprehensive cognitive and psychosocial battery as well as amyloid PET imaging. The DLBS participants (current age range: 38 - 96) allows us to address directly the role of tau deposition in declining cognition in a sample that was cognitively normal at the start of the

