6.5.2. Secondary Objectives

- **6.5.2.1.** To assess the relationship of tau burden to hippocampal volume and cortical thickness and their contributions to predicting decline in memory and other cognitive functions.
- **6.5.2.2.** To determine whether rate of amyloid accumulation over the past 8 10-year interval predicts tau deposition.
- **6.5.2.3.** To examine the detrimental effect of tau deposits, as well as the joint effect of tau and amyloid, on changes in brain activity and cognitive function.
- **6.5.2.4.** To examine differences in cognitive, structural, and functional decline between those with and without amyloid and tau pathology.

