6.10.1.2. Secondary Endpoints

Tau deposition will be estimated from Wave 3 data by the SUVr of [¹⁸F]AV-1451 in temporal regions (both left and right) of interest: (1) inferior temporal gyrus, (2) middle temporal gyrus, (3) superior temporal gyrus, (4) entorhinal cortex, (5) parahippocampal gyrus, and (6) fusiform gyrus. Amyloid accumulation will be measured as the SUVr value averaged across eight cortical regions: dorsal lateral prefrontal cortex, orbitofrontal cortex, lateral parietal cortex, posterior cingulate cortex, anterior cingulate cortex, precuneus, lateral temporal cortex, and occipital lobe. Both measures of tau and amyloid will be used as continuous measures rather than positive and negative dichotomy. In addition, there were 60 participants in Wave 2 who received tau imaging four years earlier. Change in tau deposition will be estimated for all returning participants who were among those that received tau imaging in both Waves 2 and 3. We also note that for all endpoints described below, we will analyze the data exclusively from Wave 3 in cross-sectional analyses, and then will also calculate change in all of these endpoints from Wave 1 to 3, and then retrospectively relate tau levels to changes in these endpoints.

- **6.10.1.2.1.** Hippocampal volume and regional cortical thickness will be estimated using FreeSurfer (ver. 5.3), with surface parcellation manually edited, when necessary, by our team of experts.
- **6.10.1.2.2.** Estimates of white matter integrity will be collected using diffusion tensor measures. For functional measures, BOLD signal from contrasts of interest using selected ROI's will be created using our

subsequent memory task and semantic judgment task and their relationship to tau deposition will be assessed. In addition, we will also use resting state data to look at how tau effects functional brain connectivity.

- **6.10.1.2.3.** Joint effects of tau and amyloid will be examined by including them as an interaction term in a linear mixed-model analysis.
- 6.10.1.2.4. Cognitive decline will be assessed using the following constructs: processing speed, episodic memory, working memory, and executive function. Scores on these constructs will be averaged across relevant DLBS tasks and standardized based on performance at the beginning of this longitudinal study (Wave 1).

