6.10.3. Data Analyses

For all analyses, testing the primary and secondary objectives of this study, our measures of interest will be measured continuously and entered into linear regression or linear mixed-models analyses as appropriate. For each objective, as we have noted earlier, we will first analyze the data cross-sectionally within Wave 3 to determine whether tau SUVr is related with our dependent variables. A test-wise alpha of 0.05 will determine finding significance regarding research hypotheses, and post hoc analyses will be corrected for family-wise error using the multi-stage Holm-Bonferroni method (Holm, 1979). Then we will model changes from Waves 1 - 3 in endpoints and their relationship to tau at Wave 3.

- **6.10.3.1.** Our primary objective, to determine the time course of tau deposition with age, will be first assessed by computing a linear regression between the AV-1451 SUVr in each of our temporal regions of interest with participant age. Next, we will determine whether this relationship is better fit by a quadratic, exponential, or growth model. We predict that tau accumulation will accelerate in old age, thus supporting a non-linear rate of deposition.
- **6.10.3.2.** A linear mixed-model analysis will be used to relate our continuous SUVr measure of amyloid deposition with the SUVr for tau deposition in each of our temporal ROIs. An amyloid SUVr x time of testing interaction term will be used to predict changes in tau SUVr. We predict that increased amyloid burden will be associated with accelerated tau deposition.
- **6.10.3.3.** To determine differences in cognitive, structural, and functional decline between those with and without tau and amyloid pathology, we will perform multiple linear mixed-model analyses. All variables of interest will be included as continuous measures. Tau SUVr x time and amyloid SUVr x time interaction terms will be entered in these models to predict how amyloid and tau pathology predicts longitudinal changes in our cognitive, structural, and functional measure of interest. In line with recent research, we predict tau burden in particular to be strongly associated with more rapid structural and cognitive decline.

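### The decline models in 6.10.3.3 appear to estimate amyloid's association only after adjustment for tau, so the amyloid half of objective 6.5.2.4 has no overall estimate

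*Combined protocol and SAP*

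**What the plan says.** Objective 6.5.2.4 is "To examine differences in cognitive, structural, and functional decline between those with and without amyloid and tau pathology". The matching analysis, 6.10.3.3, plans multiple linear mixed models with all variables continuous, and states that "Tau SUVr x time and amyloid SUVr x time interaction terms will be entered in these models". It then gives the expected result: "we predict tau burden in particular to be strongly associated with more rapid structural and cognitive decline".

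The rationale (6.4.4) cites, as one prevailing theory, that "amyloid induces tau tangle pathology, and it is tau that directly connects to neurodegeneration and cognitive decline". Section 6.10.3.2 adopts the first link of that chain as a prediction: "We predict that increased amyloid burden will be associated with accelerated tau deposition".

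Tau also gets analyses of its own. The Wave 3 cross-sectional step is to "determine whether tau SUVr is related with our dependent variables", and 6.10.1.2 adds that the analysts will "retrospectively relate tau levels to changes in these endpoints". Section 6.10.1 lists amyloid among the predictors of Wave 3 cognitive function, but that is a cross-sectional analysis and not one of decline.

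**The concern.** If amyloid leads to tau and tau leads to decline, tau lies on the path from amyloid to decline. With tau x time in the model, the amyloid x time coefficient is the part of amyloid's association with decline that tau does not carry. A small coefficient is then what the cited theory predicts. It is not evidence that people with more amyloid decline no faster.

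Two things are at stake. First, 6.5.2.4 asks about decline by amyloid as well as by tau pathology, and the adjusted coefficient alone may give a misleadingly small answer for amyloid. Second, 6.10.3.3 makes a comparative prediction about tau, while 6.10.3 judges findings at a test-wise alpha of 0.05 and plans no test comparing the two coefficients. One term being significant while the other is not could be taken as confirming that prediction.

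**Working it through.** **Is there an amyloid-only decline model elsewhere?** Going through the numbered analyses in 6.10.3:

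- 6.10.3.1: tau against age.
- 6.10.3.2: amyloid predicting tau. This is the first link only; decline is not the outcome.
- 6.10.3.3: both interactions, on the natural reading.
- 6.10.3.4: tau with hippocampal volume and cortical thickness.
- 6.10.3.5: the three-way product of tau, amyloid and time, so tau is again in the model.

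None gives amyloid's association with longitudinal decline without tau.

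**The plan's own power figure.** Section 6.10.2 gives 0.93 for r = 0.30 and n = 125. By Fisher z, two-sided 0.05: atanh(0.30) x sqrt(122) = 0.3095 x 11.045 = 3.419; 3.419 - 1.960 = 1.459; power = 0.928. The noncentral F gives 0.937. The figure reproduces, but it is for a single linear relationship.

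**Carrying it to the joint model.** Work in standardized units with the individual decline slope as outcome:

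- a = amyloid-tau correlation (assumed; not in the documents)
- b = tau coefficient given amyloid
- c = amyloid coefficient given tau
- overall amyloid association = c + a x b, set to the protocol's 0.30
- R² = b² + c² + 2abc
- partial correlation of amyloid = c sqrt(1 - a²) / sqrt(c²(1 - a²) + 1 - R²)
- power from the noncentral F with 1 and 122 degrees of freedom, noncentrality 125 x pr²/(1 - pr²), where pr is the partial correlation

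*Half shared with tau, a = 0.5.* Then b = 0.30 and c = 0.15; check: 0.15 + 0.5 x 0.30 = 0.30. R² = 0.09 + 0.0225 + 0.045 = 0.1575. Partial correlation = 0.1299 / sqrt(0.0169 + 0.8425) = 0.140. Power for amyloid is 0.35 by formula and 0.34 by simulation (5,000 replicates). Power for tau is 0.88 by formula and 0.87 by simulation.

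*All shared, a = 0.5.* Then b = 0.60 and c = 0. The expected amyloid coefficient is 0, so it is significant 5% of the time; tau is significant about 100% of the time.

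*Amyloid power in the joint model over a range of a* (without tau it is about 0.93 throughout):

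| Share carried by tau | Amyloid coefficient | a = 0.3 | a = 0.5 | a = 0.7 |
|---|---|---|---|---|
| None | 0.30 | 0.91 | 0.86 | 0.70 |
| Half | 0.15 | 0.49 | 0.35 | 0.24 |
| Three quarters | 0.075 | 0.24 | 0.13 | 0.10 |
| All | 0 | not feasible | 0.05 | 0.05 |

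**The comparative claim.** In the half-shared case at a = 0.5, amyloid's overall association (0.30) equals tau's coefficient (0.30). Simulation of the joint model gives tau significant and amyloid not in 62% of replicates, while a test of the difference between the coefficients is significant in 14%. A separate run of 20,000 replicates gave 60% and 15%.

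**Check for a spurious tau effect.** With b = 0 and c = 0.30, the tau term is significant 5% of the time, which is the nominal rate.

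**The case against.** Much can be said for the plan.

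- A reader might infer that the joint model is biased towards tau. It is not: with no tau effect it rejects for tau at 5%. If tau carries all of amyloid's association, singling out tau as the more direct correlate is correct. This stands.
- A reader might take 6.4.1 as asking for amyloid's independent contribution. Its words are "understand the independent and joint contributions of tau to cognitive decline and early AD at different ages", which concern tau, and for tau's independent contribution the amyloid-adjusted model is the appropriate one. This stands too.
- Joint entry is not explicit. The plan speaks of multiple analyses and of models in the plural, which leaves room for separate models. But none is described, so the gap remains until the text says otherwise.
- Objective 6.5.2.4 does not say whether it wants an overall or an adjusted contrast, and no passage says that a null amyloid term means no amyloid effect. That is fair. It is a reason to state which estimate answers the objective, because the adjusted one alone answers the amyloid half poorly under the cited theory.
- Read together, 6.10.3.2 and 6.10.3.3 cover both links of the chain. They do, but they are never combined into an estimate of amyloid's association with decline.
- The sizes rest on assumed correlations, use slopes without an age term, and are largest in the extreme case. With nothing shared, amyloid's power in the joint model is still 0.70 to 0.91.
- A reader might want a causal split into total and direct effects. The design cannot give one: tau is measured at Wave 3, at the end of the decline being modelled, and only 60 participants had tau imaging at Wave 2.

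**Conclusion.** The point holds as a gap in the analysis and its interpretation, not as a fault in the joint model. On the natural reading of 6.10.3.3, amyloid's association with longitudinal decline is estimated only with tau in the model, and that estimate does not by itself answer the amyloid half of 6.5.2.4 if amyloid acts through tau.

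The size depends on two quantities that the documents do not give: the amyloid-tau correlation and the share of amyloid's association that tau carries. With a correlation of 0.5 and an overall association of 0.30, detection of amyloid falls from about 93% to about 34% if half is shared and to 5% if all is shared.

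The documents do not support the stronger inferences that the model manufactures a tau finding or that the sponsor intends to dismiss amyloid. The matter touches secondary objectives only, since the primary endpoint is completion of the scans. It should still be corrected, because the change is small and alters what can be concluded.

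**What to change.** In 6.10.3.3, state that for each outcome two models will be fitted: (a) amyloid x time without tau x time, and (b) both terms. Report both amyloid coefficients with intervals, (a) as the overall association and (b) as the tau-adjusted association. Say that both bear on the amyloid half of 6.5.2.4 and that a null in (b) will not be read as no amyloid association.

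Base any statement that tau matters more on an interval or test for the difference between the standardized tau and amyloid coefficients in (b), not on one being significant and the other not.

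Word all of this as association, given when tau is measured. A participant-level bootstrap of the change in the amyloid coefficient from (a) to (b) is optional.

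The cost is one extra model per outcome and a somewhat harder test for the tau-specific claim. No new data are needed. If separate models were already intended, a sentence saying so closes the first part.

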6.11. STUDY MANAGEMENT

6.11.1. Conflict of Interest

Any investigator(s) who has a conflict of interest with this study (patent ownership, royalties, or financial gain greater than the minimum allowable by their institution, etc.) must have the conflict reviewed by the UTSW COI Committee and IRB according to UTSW Policy on Conflicts of Interest. All investigators will follow the University conflict of interest policy.

6.11.2. Institutional Review Board (IRB) Approval and Consent

It is expected that the IRB will have the proper representation and function in accordance with federally mandated regulations. The IRB must approve the consent form and protocol.

In obtaining and documenting informed consent, the investigator(s) should comply with the applicable regulatory requirement(s), and should adhere to Good Clinical Practice (GCP) and to ethical principles that have their origin in the Declaration of Helsinki.

Before recruitment and enrollment onto this study, the subject will be given a full explanation of the study and will be given the opportunity to review the consent form. Each consent form must include all the relevant elements currently required by the FDA Regulations and local or state regulations. Once this essential information has been provided to the subject and the investigator(s) is assured that the subject understands the implications of participating in the study, the subject will be asked to give consent to participate in the study by signing an IRB-approved consent form.

Prior to a patient's participation in the trial, the written informed consent form should be signed and personally dated by the subject and by the person who conducted the informed consent discussion.

6.11.3. Registration/Randomization Procedures

Each newly consented subject will be numbered based on their assigned Dallas Lifespan Brain Study Number. This number is unique to each subject and independent of all personal identifying information.

This study does not require randomization; all participants will receive [18F]AV-1451.

6.11.4. Data Management and Monitoring/Auditing

6.11.4.1. Regulatory Documentation

The following regulatory documents will be retained.

- A copy of the official IRB approval letter for the protocol and informed consent.
- IRB Federal-wide Assurance letter.

- CVs and medical licensure for the principal investigator and any associate investigators who will be involved in the study.
- Form FDA 1572 appropriately filled out and signed with appropriate documentation
- A copy of the IRB-approved consent form.

6.11.4.2. CRFs and Source data

Case report forms (CRFs) will be used for this trial. Individual patient files should include appropriate source documents, including but not limited to patient's medical records and laboratory test results. The files should include information such as visit dates, records of medical history, examinations administered, laboratory, concomitant treatment, any adverse event encountered and other notes as appropriate. These constitute "source data". All entries on the CRFs must be backed up by source data. Original electronic versions of imaging studies are also considered source data and will be kept on file by the site/imaging center.

Each patient's source file should include an original signed informed consent form. When the trial is completed, the informed consent form should be kept on file with other trial related records.

All original laboratory reports must be available for review in each patient's file. It is important that the original reports be available for review because of the possibility of inaccuracies or errors in transcribing data from original records to the CRF.

The CRFs must be kept in order and up-to-date so that they always reflect the latest observations on the subjects that are enrolled in the trial. The CRFs must be completed for each patient enrolled in the trial. This should be done as soon as possible after completion of the patient's participation in the trial. A monitor will verify the source data for all information on the CRF.

6.11.5. Monitoring

Trial monitoring will be conducted no less than annually and refers to a regular interval review of trial related activity and documentation performed by monitor. This review includes but is not limited to accuracy of case report forms, protocol compliance, and AE/SAE management and reporting. Documentation of trial monitoring will be maintained along with other protocol related documents and will be reviewed during internal audit.

6.11.6. Adherence to the Protocol

Except for an emergency situation, in which proper care for the protection, safety, and well-being of the study subject requires alternative treatment, the study shall be conducted exactly as described in the approved protocol.

- **6.11.6.1. Exceptions** (also called single-subject exceptions or single-subject waivers): include any departure from IRB-approved research that is not due to an emergency and is:
 - intentional on part of the investigator(s); or
 - in the investigator(s)'s control; or
 - not intended as a systemic change (e.g., single-subject exceptions to eligibility [inclusion/exclusion] criteria)
 - **Reporting requirement**: Exceptions are non-emergency deviations that require *prospective* IRB approval before being implemented. Call the IRB if your request is urgent. If IRB approval is not obtained beforehand, this constitutes a major deviation.
- **6.11.6.2. Emergency Deviations:** include any departure from IRB-approved research that is necessary to:
 - avoid immediate apparent harm, or
 - protect the life or physical well-being of subjects or others
 - **Reporting requirement**: Emergency deviations must be promptly reported to the IRB within 5 working days of occurrence.
- **6.11.6.3. Major Deviations** (also called **violations**): include any departure from IRB-approved research that:
 - Harmed or placed subject(s) or others at risk of harm (i.e., did or has the potential to negatively affect the safety, rights, or welfare of subjects or others), or
 - Affect data quality (e.g., the completeness, accuracy, reliability, or validity of the data) or the science of the research (e.g., the primary outcome/endpoint of the study)
 - **Reporting requirement**: Major deviations must be promptly reported to the IRB within 5 working days of PI awareness.
- **6.11.6.4. Minor Deviations:** include any departure from IRB-approved research that:

- Did not harm or place subject(s) or others at risk of harm (i.e., did not or did not have the potential to negatively affect the safety, rights, or welfare of subjects or others), or
- Did not affect data quality (e.g., the completeness, accuracy, reliability, or validity of the data) or the science of the research (e.g., the primary outcome/endpoint of the study)
 - **Reporting requirement**: Minor deviations should be tracked and summarized in the progress report at the next IRB continuing review.

